## **3. Quality Assurance**

### 3.1 Training requirements

The technician requires no special qualifications for performing this assessment. Training includes:

- Read and study manual
- Attend Living Well training session on techniques
- Practice on other staff or volunteers
- Discuss problems and questions with local expert

### 3.2 Certification requirements

- Complete training requirements
- Measure LDL on 2 volunteers according to protocol

### 3.3 Quality assurance checklist

- Explains procedure
- Obtains sample per "Obtaining Blood Samples" section of manual
- Obtains adequate blood sample
- Properly inserts Test Strip into analyzer
- Properly applies blood to the Test Strip
- Records LDL value on the Biometric Data Collection Form appropriately
- Discards used Test Strip
- Removes and discards Strip prior to obtaining next sample

# Weight Measurement

## 1. Equipment and Supplies

- Homedics SC-540 LCD 400 lb/180 kg Capacity Bath Scale

### 1.1 Maintenance

- When not in use the scale should be set to “off”
- Do not store anything on top of the scale
- At the end of each day, and as needed, wipe exposed parts with soft, slightly damp cloth

### 1.2 Accuracy Check

- On a monthly basis, the scale should be checked against a known 50kg weight
- Notify principal investigator there is great than a 1.0 pound discrepancy

## 2. Participant and Exam Room Preparation

The scale should be placed on a level, uncarpeted floor. If bare floor is unavailable, firm, non-compressible carpeting (e.g., indoor-outdoor) is acceptable.

Weight is measured without shoes or heavy jewelry. Study participants will be encouraged to empty their bladders and/or bowels prior to the measurement.

## 3. Measurement Procedures

**Script:** *“The measurement that we are about to take is more accurate if you use the bathroom before we measure you. If you need to use the bathroom it is down the hall.”*

- 1) Ask participant to step on the scale, positioning feet evenly on the scale platform
- 2) Display will show “HI”
- 3) Ask participant to stay still while weight is determined
- 4) Display will flash and then show weight
- 5) Repeat to confirm reading
- 6) Record value on Biometric Data Collection Form next to “weight”

**Note:** if the on/off button is pressed prior to standing on the scale, the scale will be prepared to measure body composition. Press on/off or wait 30 seconds for the scale to turn off and follow instructions above.

If a participant requires support from a cane while being weighed, weigh yourself with and without the participant’s cane, etc., to determine its weight. Subtract the weight of the aid from the participant’s weight before recording. In the event that it is necessary for the examiner to support the participant during weighing, provide the minimum support that is safe.

### **Error messages on scale**

Err	Weight Mode: unstable weight, begin again
O_Ld	Weight overload, remove weight immediately
Lo	Low battery, replace

#### 4.1 Training requirements

The technician requires no special qualifications for performing this assessment. Training includes:

- Read and study manual
- Attend Living Well training session on techniques
- Practice on other staff or volunteers
- Discuss problems and questions with local expert

#### 4.2 Certification requirements

- Complete training requirements
- Conduct exam on 2 volunteers

#### 4.3 Quality assurance checklist

- Participant encouraged to use bathroom prior to measurement
- Explains procedure
- Measurement made without shoes, heavy jewelry, or other clothing
- Ensures that participant stands still in center of platform
- Completes Biometric Data Collection Form appropriately

# Height Measurement

## 1. Equipment and Supplies

- Seca 214 Portable Stadiometer

## 2. Participant and Exam Room Preparation

Assemble Seca 214 Stadiometer by firmly inserting the height rod into the floor plate and affixing the horizontal arm to the height rod. The stadiometer should be placed on a level, uncarpeted floor. If bare floor is unavailable, firm, non-compressible carpeting (e.g., indoor-outdoor) is acceptable. There should be about a foot or more of unoccupied wall space on either side of the stadiometer.

The participant should be relaxed. He should also be barefoot or wearing thin socks or stockings. Ask the participant to remove any hairpiece or rearrange any hair styling that might interfere with firm contact between the headboard and the scalp.

## 3. Measurement Procedures

### 3.1 General Issues

To perform this measurement accurately, it is important that the recorder observe both the position of the participant and of the stadiometer. The participant should be instructed to avoid slouching and the stadiometer brought down in the midline of the head.

[figure not shown]
### 3.2 Administration

- 1) Have the participant stand in the center of the foot plate with their heels together and their back against the height rod. The back (scapulae), buttocks and both heels should be touching the height rod. Be sure that the participant maintains the correct posture during the measurement.

**Script:** *“Please stand with your back against the board mounted on this wall. Your legs should be together and your heels, your buttocks and your back should be touching the wallplate. Look straight ahead and stand tall.” If necessary to achieve Frankfort Horizontal Plane: “Please raise/lower your chin.”*

**Note:** The participant should be standing with head erect and in the Frankfort horizontal plane (see Figure 2), but, in general, the back of the head does not need to be in contact with the wall-plate. Check that the participant is in the correct position, starting with the heels and checking each point of contact with the wall-plate.

Check that the arms are relaxed and hanging loosely at the sides and that the shoulders are relaxed by running your hands over them and feeling the relaxed trapezius muscle. The head should be in the “Frankfort Horizontal Plane” in which the lowest point on the inferior orbital margin (orbitale) and the upper margin of the external auditory meatus (tragion) form a horizontal line (Figure 2). To verify that the head is in the Frankfort plane, hold the base of a clear plastic right angle (or T of a T-square) against the wall and make sure that the edge perpendicular to the wall is parallel to the “Frankfort Horizontal Plane”.

- 2) Bring the horizontal bar down firmly onto the top of the participant's head. It may be necessary, upon occasion, to alter the hair styling of some of the participants for the horizontal arm to make contact with the top of the scalp.
- 3) Have the participant breathe in deeply. They should not alter their position by, for example, raising the heels off the floor as they breathe in.

**Script:** *"Take a deep breath."*

- 4) Just before the participant exhales, note the reading on the stadiometer to the nearest 0.5cm (round down).

**Script:** *"Breathe out."*

- 5) Have the participant step away from the stadiometer, then step back in to the measurement position. Repeat steps 1 - 4 and take a second measurement.
- 6) If the two measurements differ by  $\geq 4$  mm, take an additional two measurements.
- 7) Record value on Biometric Data Collection Form next to "height" in inches and centimeters.

### 3.3 Deviations and exceptions to standard positioning:

Obese participants and those with a kyphotic posture may be unable to place heels, buttocks, and scapulae in a single vertical plane. These participants may be positioned so that only the buttocks, and possibly the scapula, are in contact with the wall-plate. The essential point is that the participant stand erect with the buttocks in contact with the wall plate and the legs as close together as possible. In very obese participants, if it is not possible to obtain contact between the headboard and the top of the skull, then the participant may need to lean back slightly (without tilting the head) until proper contact can be made.

For participants with severe spinal curvature, if the spine protrudes farthest, then that should be the part that is touching the wall plate, together with heels and buttocks. For participants with extreme kyphotic posture, it may not be possible to obtain contact between the headboard and scalp when the participant's back is against the wall-plate. In this case, measure height with the participant standing sideways (side of arm and shoulder in contact with the wall-plate) and positioned so that the headboard contacts the scalp. If the participant has 'knock-knees' then have them separate the heels so that the knees are in contact but do not overlap. Obese participants may also not be able to stand comfortably with the heels touching and may stand with the legs together and the heels separated.

## 4. Quality Assurance

### 4.1 Training requirements

The technician requires no special qualifications for performing this assessment. Training includes:

- Read and study manual
- Attend Living Well training session on techniques
- Practice on other staff or volunteers
- Discuss problems and questions with local expert

### 4.2 Certification requirements

- Complete training requirements
- Conduct exam on 2 volunteers

### 4.3 Quality assurance checklist

- Correct assembly of Seca 214 Stadiometer
- Explains procedure
- Hairpiece removed, hair style altered, if necessary
- Checks that heels are together
- Checks for heels, buttock, scapula touching wall-plate (all touching if possible)
- Two more measurements made if first two differ by  $\geq 4$  mm
- Completes Biometric Data Collection Form appropriately

## **Medication List**

The investigators and Peers require an accurate list of medications taken by the participants. This is a seemingly simple task, but can actually be challenging because participants may bring in medications they no longer take, not bring their insulin, take their medications in a way different than written on the prescription, or not bring their medications with them. There are special instructions for aspirin and insulin below.

The biometrics personnel must:

1. Generate as accurate a medication list as possible
2. Keep one copy for the researchers, make a copy for the participant, and if the participant is assigned a Peer, make a copy for the Peer

# 1. Instructions

## **If the participant has brought their medications, check the “Yes” box next to “Brought Medications” and for each medication:**

1. Ask if the participant takes that medication
2. Ask if the participant take it as it is written on the prescription bottle.  
*This is not meant to be a negative question and should not be asked in a way that assumes non-adherence. Sometimes doctors prescribe twice the dose and ask the patient to cut it in half to save the patient money, or they write for it to be take daily even though the patient only takes it “as needed” so that a “one month” supply lasts longer.*
3. Record the medication (start on the #1 line, unless the medication is aspirin or insulin)
  - a. Name
  - b. Dose
  - c. How often taken
4. Ask if the patient takes any other medications, either prescription or over-the-counter
  - a. If so, follow directions for participant’s who did not bring their medications (below)
5. If aspirin has not already been documented, ask if the patient takes aspirin
  - a. If not, check the “no” box next to “Aspirin”
  - b. If so, check the “yes” box follow and directions for aspirin (below)
6. If insulin has not already been documented, ask if the patient takes insulin
  - a. If not, check the “no” box next to “Insulin”
  - b. If so, check the “yes” box and follow directions for insulin (below)

Brought medications	 No	 Yes	
Aspirin	 No	 Yes	81 mg per day or _____  from memory (circle)
Insulin	 No	 Yes	

## **If the participant did not bring their medications** check the “no” box next to “brought medications” and:

1. Ask if the participant knows his/her medications
  - a. If yes, write down as much as the participant knows of the medications’
    - i. Name
    - ii. Dose
    - iii. How often take
  - b. Check the “From memory” box on each line in which the medication information is based solely on participant recall
2. Prompt for prescription, over-the-counter medication, aspirin, and insulin.

**Aspirin**, people often do not consider aspirin as a real medication and they often do not bring it with them. So the top of the Medication List has a space specifically to prompt about aspirin. Most people with diabetes should be taking an aspirin and most will be taking 81mg daily.

1. If the participant brought aspirin, check the “yes” box next to “Aspirin” and
  - a. circle “81mg per day” if correct
  - b. or cross out “81mg per day” and write in the dose/frequency the patient is taking
2. If the participant did not bring aspirin ask if the participant takes aspirin and check the boxes accordingly

**Insulin**, since insulin is stored in a glass vial and in the fridge, participants often forget to bring their insulin. And the directions are often not written on the insulin, so you will have to ask the participant how the insulin(s) are taken. Most people take one or two types of insulin (insulin names are listed below). We have left 3 lines for insulin at the top of the medication list.

1. Ask if the participant takes insulin and check the appropriate box.

If “yes”,

2. If the participant brought insulin(s)
  - a. Write the name
  - b. Ask how much and how often the insulin is injected
    - i. If the participant knows, record and do not check the “From Memory” box
    - ii. If the participant does not know either the dose or the frequency
      1. Record what the participant does know
      2. Write “?” for information the participant doesn’t know
      3. Check the “From Memory” box
3. If the participant did not bring insulin,
  - a. Ask if the participant knows the type, dose, and frequency of insulin(s) taken
    - i. If participant knows all 3, record and do not check “From Memory” box
    - ii. If the participant does not know
      1. Record what the participant does know
      2. Write “?” for information the participant doesn’t know
      3. Check the “From Memory” box
      4. You may prompt participant with names of different insulins if he/she thinks that will help them remember
4. Sliding scales. Some participants may not be on a fixed insulin dose, but may take a different amount of insulin depending on their glucose reading. Those people usually are also taking a fixed-dose long-acting insulin. Record the fixed doses and write S/S for sliding scale (example on next page). Do not check “From Memory” box.
5. Insulin pump. Some participants may be using an insulin pump. We do not need dosages or frequencies for those participants (example on next page). Do not check “From Memory” box, even if they do not know the name of the insulin in their pump.

### Types of Insulins, trade name (and generic name)

#### Combination insulins usually taken once or twice per day

- Humalin 70/30 (NPH/regular insulin)
- Humalin 50/50 (NPH/regular insulin)
- Novalog 70/30 (insulin aspart protamine/ insulin aspart)
- Humalog 50/50 (insulin lispro protamine/ insulin lispro)
- Humalog 75/25 (insulin lispro protamine/ insulin lispro)

#### Long-acting insulins usually taken one or twice per day

- Humalin N (NPH insulin)
- Novalin N (NPH insulin)
- Lantus (insulin glargine)
- Levemir (insulin detemir)

#### Short-acting insulins usually taken several times per day or used in an insulin pump

- Humalin R (regular insulin)
- Novalin R (regular insulin)
- Humalog (insulin lispro)
- Novalog (insulin aspart)
- Apirdra (insulin glulisine)

**Knows the name and frequency, but not the dose**

	medication	dose	frequency	notes	from memory
insulin	70/30	?	Twice a day		
					
					

**Knows frequency and dose, but not the name**

	medication	dose	frequency	notes	from memory
insulin	?	10 units	at night		
	?	5 units	with meals		
					

**Only knows dosage**

	medication	dose	frequency	notes	from memory
insulin	?	10 units	?		
					
					

**Only knows frequency**

	medication	dose	frequency	notes	from memory
insulin	?	?	twice a day		
					
					

**Sliding scales**

	medication	dose	frequency	notes	from memory
insulin	Lantus	20 units	every night		
	Novolog	s/s	twice a day		
	Novolog	s/s	as needed		

**Insulin pump and doesn't know the type of insulin**

	medication	dose	frequency	notes	from memory
insulin	?	pump	pump		
					
					

### **3. Quality Assurance**

#### 3.1 Training requirements

The technician requires no special qualifications for performing this assessment. Training includes:

- Read and study manual
- Attend Living Well training session on techniques
- Practice on other staff or volunteers
- Discuss problems and questions with local expert

#### 3.2 Certification requirements

- Complete training requirements
- Generate a medication list for 2 volunteers according to protocol

#### 3.3 Quality assurance checklist

- Ascertains if the participant brought his/her medications
- Ascertains if the participant takes his/her medications as written on the bottles
- Probes for over-the-counter, aspirin, and insulin use
- Gathers as much information as possible if participant did not bring medications
- Checks the “from memory” box when the participant did not bring medications
- Completes Medication List form appropriately

# Report Card

The participants will receive a report card providing the results from the biometrics exam. Biometrics personnel will also provide basic interpretation of the values, but in depth questions need to be referred to the participant's physician.

## Report Card

There are some things you can do to reduce the health risk of diabetes.

These numbers can give you an idea of how you are doing.

You may want to talk to your doctor...

### A1C (Average Sugar Control over the last 3 months)

 Great control	Less than 7
 Ok, not perfect	7.0 ↔ 7.9
 Cause for concern	8.0 ↔ 8.9
 Bigger cause for concern	> 9.0

---

### Blood Pressure

 Normal	Less than 120/80
 Our Goal	Less than 140/90
 High-talk to doctor	140/90 or higher

---

### Cholesterol (LDL cholesterol or your "bad cholesterol")

 Okay	Less than 100
 High-talk to doctor	100 or higher

---

### Weight

 Normal (excellent)
 Overweight (may be concerning)
 Obese (take action)

## 1. Completing the Report Card

### 1) A1c

- Transcribe the A1c value from the Biometric Data Collection Form onto the Report Card
- Place a check mark in the appropriate box (if A1c < 7.0 great control, 7-7.9 okay, 8-9 Concerning, and >9 bigger concern).

### 2) LDL

- Transcribe the LDL value from the Biometric Data Collection Form onto the Report Card
- Place a check mark in the appropriate box.

### A1C (Average Sugar Control over the last 3 months)

8.1

 Great control	Less than 7
 Ok, not perfect	7.0 ↔ 7.9
 Cause for concern	8.0 ↔ 8.9
 Bigger cause for concern	> 9.0

### Cholesterol (LDL cholesterol or your "bad cholesterol")

150

 Okay	Less than 100
 High-talk to doctor	100 or higher

### 3) Blood Pressure

- Transcribe the lowest of the 2 research blood pressure reading values from the Biometric Data Collection Form onto the Report Card.
- Use the systolic value to determine the blood pressure category and place a check mark in the appropriate box (if SPB < 120 normal, <140 our goal, and >140 High)

Blood Pressure	
145/78	 Normal Less than 120/80
	 Our Goal Less than 140/90
	 High-talk to doctor 140/90 or higher

### 4) Weight

- Transcribe the weight in pounds from the Biometric Data Collection Form onto the Report Card.
- Find the participant's height on the Height-Weight Reference Sheet and write the ranges next to Normal, Overweight, and Obese.
- Place a check mark in the appropriate box for Normal, Overweight, and Obese.

Weight	
175	 Normal 100-135 <small>(excellent)</small>
	 Overweight 136-160 <small>(may be concerning)</small>
	 Obese >160 <small>(take action)</small>

### Height - Weight Ranges

 
Normal <small>(excellent)</small>	
 
Overweight <small>(may be concerning)</small>	
 
> Obese <small>(take action)</small>	
 
	Normal <small>(excellent)</small>	Overweight <small>(may be concerning)</small>	> Obese <small>(take action)</small>	
 
120 ↔ 160	
 
161 ↔ 200	
 
> 200	
 
	120 ↔ 160	161 ↔ 200	> 200
Normal <small>(excellent)</small>							
Overweight <small>(may be concerning)</small>							
> Obese <small>(take action)</small>							
120 ↔ 160							
161 ↔ 200							
> 200							

 
90 ↔ 125	
 
126 ↔ 150	
 
> 150	
 
	90 ↔ 125	126 ↔ 150	> 150	
 
130 ↔ 180	
 
181 ↔ 215	
 
> 215	
 
	130 ↔ 180	181 ↔ 215	> 215
90 ↔ 125							
126 ↔ 150							
> 150							
130 ↔ 180							
181 ↔ 215							
> 215							

 
100 ↔ 135	
 
136 ↔ 160	
 
> 160	
 
	100 ↔ 135	136 ↔ 160	> 160	
 
145 ↔ 190	
 
191 ↔ 230	
 
> 230	
 
	145 ↔ 190	191 ↔ 230	> 230
100 ↔ 135							
136 ↔ 160							
> 160							
145 ↔ 190							
191 ↔ 230							
> 230							

 
110 ↔ 145	
 
146 ↔ 180	
 
> 180	
 
	110 ↔ 145	146 ↔ 180	> 180	
 
150 ↔ 210	
 
210 ↔ 245	
 
> 245	
 
	150 ↔ 210	210 ↔ 245	> 245
110 ↔ 145							
146 ↔ 180							
> 180							
150 ↔ 210							
210 ↔ 245							
> 245							

### 6) You may want to talk to your doctor...

- Write the conditions which are in the "concerning" or "take action" ranges.

## 2. Interpreting Values for Participants

Living Well personnel should provide the results of the biometric measurements and explain what the numbers mean. Their role is not to provide medical advice. If participants have questions beyond the explanation of the values and the risks that may be associated with elevated values, participants should be instructed to talk to their health care providers. Below are suggested explanatory scripts.

### 1) A1c

Read the following text until the participant's A1c range is reached. For example, read the first 3 bullets for someone with an A1c of 6.5.]

A1c, also called hemoglobin A1c or glycosylated hemoglobin, indicates how well a person's diabetes is controlled. A1c is a blood test that indicates a person's glucose level over the last 2-3 months. Doctors order this test once a year if a person has excellent control of their diabetes and every 3 months when diabetes is not well controlled.

- People without diabetes have an A1c of about 5.
- A person with diabetes who has an A1c less than 7 is under excellent control. Their risk for diabetic complications such as damage to the blood vessels in the eyes, kidneys, heart, and brain (which can cause blindness, kidney failure, heart attack, and stroke) is low.
- Experts agree that when a person has an A1c from 7 to 8, they should do something. It may be changing their diet and exercise, starting medication, or increasing medication.
- A person with an A1c greater than 8 has poorly controlled diabetes. They are at risk for complications of diabetes. Experts recommend people with poorly controlled diabetes should have their medications increased or new medications should be started.

### 2) Blood pressure

Having high blood pressure, or hypertension, is especially troublesome when a person has diabetes. Research has shown that in people with diabetes, to protect the heart, kidneys, and brain, it is more important to control blood pressure than to control glucose. For this reason, experts suggest lower blood pressure goals for people with diabetes compared to people without diabetes. Doctors should check blood pressure at every visit.

- Although we look at both the top number, the systolic blood pressure, and the lower number, the diastolic blood pressure, a person's risk for complications is more associated with systolic blood pressure
- Your systolic blood pressure is [read only the statement coinciding to the participant's value]
  - o less than 120. So you don't need to be doing anything more than what you are already doing.
  - o less than 140 is your goal. Keep checking your blood pressure regularly, and if it goes over 140, you should speak with your doctor.
  - o greater than 140. Experts suggest that you and your doctor should take some action to decrease your blood pressure.

**NOTE:** *In the event of a hypertensive participant, the following protocol will be taken.*

- *Any participant with a blood pressure reading between 140/90 – 159/99 will be advised to talk to their doctor about their high blood pressure at their next visit with their doctor.*
- *Any participant with a BP reading between 160/100 – 179/109 will be advised to call their doctor on the same day if possible.*
- *For participant with a BP ready over 180/110, the research staff will stop and call [name]. [name] will speak with the participant develop a plan for the participant to obtain immediate medical attention.*

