## 4. Quality Assurance

Clinical experience with blood pressure measurement is required. In addition, training should include:

- Read and study manual and data collection packet
- Attend Living Well training session on techniques
- Practice on other staff or volunteers
- Discuss problems and questions with program coordinator

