**Remember to complete each page, fill out each blank, and check each item off on the list as you complete them.**

Use this packet along with the Living Well Biometric Protocol, v. 2016-May24

It is very important that you do not rush and the data that is collected is accurate. Document if anything unusual happens or if it was necessary to make changes to any of the protocol in the “Notes” sections.

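### The report-card blood pressure box and script go by systolic alone, against the card's own paired cut-offs, and the escalation NOTE has no rule for split readings

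*Combined protocol and SAP*

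**What the plan says.** Four places in Appendix F (Biometric Protocol) bear on this.

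- *Report Card, Completing the Report Card, item 3 (Blood Pressure)* tells staff: "Use the systolic value to determine the blood pressure category and place a check mark in the appropriate box". The cuts are "if SPB < 120 normal, <140 our goal, and >140 High".
- *The printed card* (Report Card, Blood Pressure box, repeated on the Health Report Card) gives paired limits. *Normal* is below 120/80, *Our Goal* is "Less than 140/90", and *High* starts at 140/90.
- *Interpreting Values for Participants, item 2 (Blood pressure)* gives a script whose statement is chosen by systolic. Its middle line is "less than 140 is your goal. Keep checking your blood pressure regularly, and if it goes over 140, you should speak with your doctor". The line for systolic below 120 tells the participant that nothing further is needed. The script's stated reason is that systolic pressure tracks complication risk more closely.
- *The NOTE under that item* sets urgency in three paired tiers. From 140/90 to 159/99 the advice is to raise it at the next visit. The second tier reads: "Any participant with a BP reading between 160/100 – 179/109 will be advised to call their doctor on the same day if possible". The top tier reads: "For participant with a BP ready over 180/110, the research staff will stop and call" a named study contact.

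The surrounding safeguards are these. The Blood Pressure quality-assurance section says: "Clinical experience with blood pressure measurement is required". The In-person Data Collection Form says: "Use this packet along with the Living Well Biometric Protocol". The form also tells collectors to halt and phone the study manager whenever a question comes up.

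**The concern.** An instruction and the card it fills in should give the same answer for every reading. Here they differ whenever diastolic pressure is raised and systolic is not. The participant can then leave with a tick beside *Our Goal* or *Normal* for a reading that the same card defines as high. The card's list of matters to raise with a doctor is built from the conditions in the concerning ranges, so a diastolic-only elevation can drop off that list as well.

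The NOTE raises a second, separate question. It decides between advice at the next visit, a same-day call and stopping the visit. Because it is written in pairs with no tie-break, two careful collectors could act differently on the same split reading.

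What is at stake is the advice given to individual participants. No estimand, power figure or error rate is touched.

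**Working it through.** **Step 1: apply the rules as written.** Each reading is classified by the systolic instruction, by the printed card, and by the NOTE under three possible meanings of a paired tier. On the printed card, a reading that fails *Our Goal* can only go to *High*, taking the 140/90 limit to be crossed when either number crosses it.

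| Reading | Box by instruction | Box by printed card | NOTE: both numbers in tier | NOTE: either number in tier | NOTE: systolic only |
|---|---|---|---|---|---|
| 130/112 | Our Goal | High | none | stop and call | none |
| 118/95 | Normal | High | none | next visit | none |
| 140/85 | none | High | none | next visit | next visit |
| 150/115 | High | High | none | next visit and stop and call | next visit |
| 165/85 | High | High | none | same day | same day |
| 185/95 | High | High | none | next visit and stop and call | stop and call |
| 180/110 | High | High | none | none | none |

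Three results follow.

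- The first two rows are direct conflicts between instruction and card: 112 and 95 are not below 90.
- Systolic exactly 140 lies between the instruction's strict cuts, although the printed card and the NOTE both include it.
- Every split reading shown gets a different NOTE action depending on how the tier is read. Exactly 180/110 is in no tier on any reading, because the second tier ends at 179/109 and the third begins above 180/110.

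The manual's worked example, 145/78 ticked *High*, comes out the same under both box rules. It would not alert a trainee to the conflict.

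**Step 2: how often the instruction and card part company.** The documents give no blood pressure distribution, so these inputs are assumptions: systolic mean 130 or 140, SD 20; correlation 0.5, 0.6 or 0.7; diastolic mean 80, SD 11, then varied. The base of 500 is one reading for each planned participant. Readings are whole mmHg, so the cuts are at half-units:

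N = 500 × P(S < 139.5 and D > 89.5), with S and D bivariate normal.

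For systolic mean 130 and correlation 0.5, the standardised cuts are (139.5 − 130)/20 = 0.475 and (89.5 − 80)/11 = 0.864. The joint probability is 0.0773, so N = 500 × 0.0773 ≈ 38.6.

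| Systolic mean | Correlation | S < 140, D ≥ 90 | of which D 90–99 | D 100–109 | D ≥ 110 |
|---|---|---|---|---|---|
| 130 | 0.5 | 38.63 | 33.96 | 4.44 | 0.224 |
| 130 | 0.6 | 32.06 | 29.05 | 2.92 | 0.097 |
| 130 | 0.7 | 24.89 | 23.33 | 1.54 | 0.026 |
| 140 | 0.5 | 20.05 | 18.07 | 1.91 | 0.076 |
| 140 | 0.6 | 14.57 | 13.55 | 1.00 | 0.023 |
| 140 | 0.7 | 9.23 | 8.86 | 0.36 | 0.004 |

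Diastolic 90–99 makes up 33.96/38.63 = 88% of the total in the first row and 8.86/9.23 = 96% in the last.

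**Step 3: vary the diastolic assumption.** With the systolic and correlation settings unchanged, diastolic mean 75 and SD 10 gives 1.4 to 10.9 per 500. Mean 85 and SD 12 gives 30.5 to 84.9. The count is therefore known only to lie somewhere between about 1 and 85.

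**Step 4: the boundary values.** Systolic exactly 140 is expected 500 × [Φ((140.5 − μ)/20) − Φ((139.5 − μ)/20)] times, which is 8.8 for mean 130 and 10.0 for mean 140. The exact pair 180/110 is expected about 0.00 to 0.04 times per 500 over all the settings.

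**The case against.** The strongest reply is that systolic priority is deliberate. The script says that both numbers are looked at and then explains why systolic carries more weight. That explains the emphasis, but it does not reconcile a systolic-only instruction with the paired definitions on the card being filled in.

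The reply is stronger on the script. Its statement is about systolic pressure and is literally true of 130/112; the scripts are described as suggestions; and the full reading is written on the card beside the 140/90 limit. This stands for the middle line. It does not rescue the line for systolic below 120, which tells someone at 118/95 that no more is needed.

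The safeguards are real. Collectors need blood pressure experience, must use the manual with the form, and must stop and ask when in doubt. Peer-arm materials use paired limits, and eligibility requires a doctor's visit within 12 months. These help with split readings under the NOTE, where the ambiguity itself should prompt a question. They help less with the card box, because the instruction gives a clear answer for 130/112 and no question need arise.

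A reader might infer that the plan causes stop-and-call cases to be missed. If staff carried the systolic rule into the NOTE, the misses per 500 (diastolic mean 80, SD 11) would be 0.8–1.6 for stop-and-call and 4.5–12.8 for at least a same-day call. The documents do not support that step. The systolic rule governs the card box, and the NOTE is worded in pairs. A reader might also object that the NOTE is not printed at the form's blood pressure step; since the form is to be used with the manual, that is a layout preference.

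**Conclusion.** The concern holds as a minor participant-safety point. The box instruction and the script conflict with the printed card whenever diastolic is 90 or more and systolic is below 140, and the instruction then gives a falsely reassuring tick. Systolic exactly 140 is left out of the instruction and the script. The NOTE leaves split readings unspecified, so the action for 130/112 or 150/115 depends on the collector.

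The size is about 9 to 39 discordant readings per 500 under the central assumptions, and about 1 to 85 when the diastolic distribution is varied. Most would lose only advice to mention the reading at the next visit. These counts illustrate scale and are not estimates for this population.

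Two further inferences are not supported. The gap at exactly 180/110 is genuine but negligible. Nor can it be said that the trial lacks an overriding blood pressure safety rule, because Part 1 of the document is not available.

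**What to change.** 1. In the Report Card instruction and the script, choose the category by the worse of the two numbers. *High* is systolic 140 or higher, or diastolic 90 or higher. *Our Goal* is below 140 and below 90. *Normal* is below 120 and below 80.
2. In the NOTE, state that the higher tier of the two numbers governs, and define the top tier as systolic 180 or higher, or diastolic 110 or higher.

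The cost is a few words in three places, some extra doctor-advice messages and a few more stop-and-call contacts. Measured against a systolic-only use of the NOTE, with diastolic mean 80 and SD 11, the change adds per 500 readings 1.7–2.6 stop-and-call contacts, a net 3.7–11.2 same-day advisories and a net 4.7–25.8 next-visit advisories. These figures would rise or fall with the diastolic assumption. They would be smaller if staff already apply the NOTE to both numbers. No change to the form's layout is needed.
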